	
 
Lay focus groups: Survivors or people with insight in to the issues and a special interest in supporting others with domestic abuse / suicidal ideation
 
Co-development workshops: Survivors or people with insight in to the issues and a special interest in supporting others with domestic abuse / suicidal ideation AND community pharmacy staff
 

	Phase 2: Feasibility Randomised Controlled Trial
	
 
Intervention / Control pharmacies: Community pharmacy staff
 
Clients (service users): people who access the intervention
 
Post-intervention pharmacy staff focus groups: community pharmacy staff in the intervention arm
 
Interviews with pharmacy customers: Regular customers who use the pharmacy
 
E-survey: General public in locality of intervention pharmacies
 
Summary workshop: Community pharmacy staff (those in the intervention arm of the study), members of the study's Patient and Public Involvement group and study management group
 

Eligibility Criteria	Phase 1: Co-development of the complex intervention
	
 
Stakeholders (representative of an organisation that supports people experiencing domestic abuse / suicidal ideation)
 
Lay survivors or those with insight of domestic abuse / suicidal ideation
 
Lay survivors or those with insight of domestic abuse / suicidal ideation
 

	Phase 2: Feasibility Randomised Controlled Trial
	
 
Intervention / Control pharmacies: Community pharmacy staff in the Lincolnshire area
 
Service users: ≥18 years
 
Post-intervention pharmacy staff focus groups: Pharmacy staff who delivered the intervention
 
Pharmacy customers: Identified as pharmacy-users and ≥18 years
 

	
 
5. E-survey: Members of the general public ≥18 years
 
6. Summary workshop: Community pharmacy staff (those in the intervention arm of the study), members of the study's Patient and Public Involvement group and study management group
 

Planned Sample Size	Phase 1: Co-development of the complex intervention
	
 
Stakeholder scoping interviews: minimum of 8 participants
 
Lay Focus groups: 2 focus groups with 8 participants in each
 
Co-production workshops: 3 workshops with 12 participants in each (Lay survivors of domestic abuse / suicidal ideation (8) AND community pharmacy staff (4))
 

	Phase 2: Feasibility Randomised Controlled Trial

Page 6 of 50

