# Phase 2: Feasibility cluster Randomised Control Trial

Pharmacy staff (to be trained, deliver the intervention, and participate in focus group and feasibility workshop)

- (a) Aged ≥18 years
- (b) Employed by a community pharmacy that is in the study

Clients (service users, (recipients of the intervention)

- (a) Aged  $\geq$ 18 years
- (b) Asking about or requiring support about domestic abuse / suicidal ideation

Pharmacy customers (for interviews)

(a) Aged  $\geq$ 18 years

(b) Familiar with the intervention pharmacy

General public (for community e-survey)

(a) Aged  $\geq$ 18 years

(b) Resident in Lincolnshire

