# STUDY PROCEDURES/REGIMEN

#### STUDY FLOWCHART

This is a two-stage development and feasibility study to develop a complex intervention.

Page 23 of 50

ENGAGEMENT	DEVELOPMENT – 6 months
Regular Study Steering Group, and Study	A. Foundations – update literature review and evidence-base, write study documentation and apply for research ethics committee approval.
Management Group meetings	B. Co-production - components of the intervention through a series of scoping interviews with a minimum of 8 key stakeholders (representatives from organisations that offer DA and SP services), followed by 2 lay focus groups and then 3 co-production
Regular Public and Patient involvement & Engagement meetings On-going collation of mailing list of interested parties, with regular distribution of	workshops with 8 lay people and 4 pharmacy staff representatives in each workshop (total of 36 participants).
	C. Modelling – finalisation of the above intervention elements, with consideration of RE_AIM (Reach, Effectiveness, Adoption, Implementation, Maintenance)  plus ethics, data monitoring and finalisation of outcomes for feasibility study.
	FEASIBILITY – 18 months
	D. Recruitment and Training - Recruit 8 x pharmacies for intervention and 2 x pharmacies as comparisons, purposive sampling to cover rural/urban, small pharmacy/commercial store and differing socio-economic areas. Recruit and train a minimum of 3 members of staff from each pharmacy in intervention (total 24 staff).
updates Project website	E. Implementation of Intervention - Promotion of the service to the public, Implement intervention in the 8 pharmacies, data collection over 6 months in 8 x intervention pharmacies and 4 x comparison (control) pharmacies.
	F. Evaluation for acceptability - Using the Theoretical Framework for Acceptability of Healthcare Interventions.  These will be investigated with pharmacy staff in 3 x focus groups with 8 staff in each (total 24 participants), followed by interviews with 2 to 3 regular customers per intervention pharmacy (not people who have use the intervention) (total 16-24 participants). An e-survey will then be designed from the qualitative analysis themes, and distributed widely to members of the public, electronically using social media, with the aim of having 600 completed surveys.

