**E. Implementation of Intervention –** The service will be promoted through a variety of settings including social media, supermarkets, pubs, community centres, sports centres, religious venues and hairdressers (depending on COVID-19 restrictions), in addition to a press release, a radio advert and the website.

The service will be implemented for 6 months (see Appendix 2 for client flow diagram). During this time the participating pharmacy staff will have monthly supervisory follow up visits from the researcher to check on fidelity of service delivery and offer support, plus access to a monthly online mentoring session with a psychotherapist to debrief on any distress that may have been incurred or any ethical issues that have been encountered.

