#### 3. Public e-survey

The themes from the combined qualitative analysis will be used to form the basis of a quantitative e-survey. The rationale of the community survey is to measure the wider awareness of the service.

The e-survey will be distributed through local community networks (the same as were used in the promotional strategy), and the intervention pharmacies, and will evaluate public awareness and attitudes towards acceptability and accessibility. The survey will contain a participant information section. A total of 600 responses will be aimed for. Assuming a response rate of 50%, 1200 people will need to be specifically targeted. Students will be employed through the University of Lincoln's "Campus Jobs" scheme to conduct market research by approaching passers-by in community settings and promoting on social media. Data from the survey will be analysed using descriptive and comparative statistics for different demographic groups.

**G. Feasibility of the intervention -** A summary workshop will be held with the 24 staff members, plus PPIE panel and Study Management Group will be held to explore the feasibility of the intervention as a possible

service and to review and finalise the intervention. Consideration will be given to: any unintended or adverse consequences, the degree of local adaptation that would be required, who would deliver the training, who would deliver the mentoring, factors that facilitate/hinder the intervention, and its overall benefits and limitations of the intervention. This would enable us to fully describe the intervention, and its components, plus the extent to which it can be adapted, so that it can be reproduced faithfully. The topic guide for the workshop will be based on the Consolidated Framework for Implementation Research. Pharmacy staff participants will receive a £75 for participating as a token of appreciation (or a voucher if preferred), as this will be an additional event after the 6 months implementation, for which the pharmacy received a fee.

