# 3. Public Questionnaires

This brief and optional e-survey will seek to measure general awareness of the service in the wider community and attitudes towards acceptability and accessibility. Participating in the questionnaire may present a minor inconvenience but has minimal physical risks or burden. Participants will be informed in the information sheet that participation is voluntary and they can choose not to answer any question.

There will also be contact details of self-help support services at the end of the questionnaire should these be needed. Return of the questionnaire will imply consent.

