33	Effectiveness of dissemination and promotion of intervention		70% of more or customer survey respondents aware of the service (intervention)	50% of more or customer survey respondents aware of the service (intervention)	30% of more or customer survey respondents aware of the service (intervention)	
34	Final consideration of the feasibility of the actual intervention. Are all the components of the intervention feasible and needed? Are there any other components that should be added?	Consideration of: 2,3,4,9,10,11,12, 14,15,16,17,18, 20,21,30,32, 33 &34 By research team, PPI panel and CTU				
35	Feasibility of a future trial – Is a trial possible?	Consideration of: 1,5,6,7,8,10,11,12, 14,15,16,17,18,19, 20,21,22,23,24,25, 26,27,28,29,30,31, 32 & 34 and questions in 35 Research team and CTU				
	What will be primary and secondary outcomes in a future cluster RCT? What are the feasible differences in primary outcome between the intervention and control groups, and the estimated intraclass correlation? Would stratification be required in the trial (type of pharmacy,					

Page 48 of 50

urban/rural location,			
socioeconomics of area,			
ethnic diversity of			
area)?			
Should sub-groups be			
considered? Is it			
feasible to randomise?			
Is it feasible to recruit			
controls?			
Power calculation and			
sample size required,			
for whole sample and			
any sub-groups.			
Possible sources of			
contamination, for			
example staff moving			
between pharmacies.			
How data would be			
analysed?			
Can quality of life,			
acceptability and			
satisfaction, and other			
health economic criteria			
be measured?			
What would be the			
requirements for future			
funding?			
	1		

 \*It is expected that should a criteria be recorded as red, this will be reviewed by the study team and adjustments made accordingly to any future design.

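### The e-survey that scores public awareness of the service is distributed through the promotion networks and the intervention pharmacies, so its sampling frame over-represents people likely to have been exposed

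*Protocol*

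**What the plan says.** The Public e-survey section (Phase 2, step F.3) gives the purpose: "The rationale of the community survey is to measure the wider awareness of the service". The section on risks of the public questionnaires repeats it, saying the survey seeks to "measure general awareness of the service in the wider community".

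On distribution, step F.3 says: "The e-survey will be distributed through local community networks (the same as were used in the promotional strategy), and the intervention pharmacies". It adds that students will approach passers-by in community settings and promote the survey on social media. The recruitment section lists supermarkets, post offices, sports venues and faith venues as survey outlets. The flowchart names social media.

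On promotion, step E says: "The service will be promoted through a variety of settings including social media, supermarkets, pubs, community centres, sports centres, religious venues and hairdressers". A press release, a radio advert and the website are added.

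Appendix 1, criterion 33, judges the effectiveness of dissemination and promotion by the percentage of "customer survey respondents aware of the service (intervention"), with 70% in the green column, 50% in amber and 30% in red. Row 34, the final consideration of the intervention, lists criterion 33 among its inputs.

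The population is described in two ways. The Study Summary has "General public in locality of intervention pharmacies"; the inclusion criteria for the general public have "Resident in Lincolnshire", and the exclusion criteria match the latter.

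On timing, the flowchart places the survey after the staff focus groups and customer interviews: "An e-survey will then be designed from the qualitative analysis themes".

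**The concern.** The wanted quantity is a proportion in the public. The respondents are sought largely where the promotion was placed and, in addition, in the pharmacies that ran the service. If awareness is higher in those channels than in the public at large, the sample proportion exceeds the public proportion however many people reply.

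This matters for interpretation as well as for the score. The primary outcome is the number of consultations. If few people consult, the team needs to know whether the service was unwanted or simply unknown. An awareness figure raised by the way the survey was distributed would point towards lack of demand when the true problem was lack of reach.

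**Working it through.** **Overlap of channels, from the protocol's own lists**

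| Channel | Promotion (step E) | Survey (step F.3, recruitment section, flowchart) |
|---|---|---|
| Social media | yes | yes |
| Supermarkets | yes | yes |
| Sports venues | yes | yes |
| Religious or faith venues | yes | yes |
| Post offices | not named | yes |
| Intervention pharmacies | site of the service | yes |
| Passers-by approached by students | not applicable | yes |

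The overlap is stated outright in step F.3, and the lists confirm it. The protocol sets no quota by channel and no weighting. The only comparisons it plans for the survey are between demographic groups.

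**Sampling error, starting from the plan's own figure**

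The Size of sample section gives 95% intervals of 8.3% to 11.7% at 10% awareness and 27.4% to 32.6% at 30%. The half-width is 1.96 × √(p(1 − p)/n).

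- n = 600 (planned responses): 1.96 × √(0.10 × 0.90/600) = 0.024, so 7.6% to 12.4%. At 30% the half-width is 0.037, so 26.3% to 33.7%. These are not the stated intervals.
- n = 1200 (people targeted at a 50% response rate): half-widths 0.017 and 0.026, which reproduce the stated intervals. That mismatch is a separate matter.
- At n = 600 and p = 50% the half-width is 0.040.

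Sampling error at 600 responses is therefore 2.4 to 4.0 points for awareness between 10% and 50%. A frame effect is not reduced by raising n.

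**Possible size of the frame effect (illustration only)**

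Let s be the share of responses from the enriched channels, pₑ the awareness in them, and p₀ the awareness in the public, which the remaining responses are taken to reflect. Then measured awareness = (1 − s) × p₀ + s × pₑ, and the excess over p₀ is s × (pₑ − p₀). Only p₀ = 10% and 30% come from the protocol, as its planning values; s and pₑ are assumptions.

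| p₀ | s | pₑ | Measured |
|---|---|---|---|
| 10% | 0.25 | 50% | 20% |
| 10% | 0.75 | 70% | 55% |
| 10% | 0.75 | 80% | 62.5% |
| 30% | 0.25 | 50% | 35% |
| 30% | 0.50 | 70% | 50% |
| 30% | 0.75 | 80% | 67.5% |

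For s from 0.25 to 0.75 and pₑ from 50% to 80%, measured awareness runs from 20% to 62.5% when public awareness is 10%, and from 35% to 67.5% when it is 30%. With pₑ only 40% and p₀ 10%, s = 0.25, 0.50 and 0.75 give 17.5%, 25% and 32.5%, all below the 50% amber figure.

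**Forces in the other direction**

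The survey is written after the post-intervention qualitative analysis, so recall may have faded. Eligibility covers the whole county, and residents living far from the eight intervention pharmacies may have had little exposure. The documents give no figure for either effect.

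**The case against.** The strongest reply is that the promotion settings are ordinary public places. People in supermarkets, sports centres and faith venues, and on social media, make up much of the general public. Students also approach passers-by, and post offices are used. On this view the only clearly enriched stream is the intervention pharmacies, whose share is unknown. Much of this stands: the frame over-represents exposed people, but it does not consist of them.

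A reader might infer that criterion 33 is biased upwards overall. The documents do not support that. Late timing and county-wide eligibility may lower the figure, and none of the components can be sized.

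A reader might also infer that the overlap is shown to lift the criterion into a better band, for instance by passing 30%. It is not. The 30% figure sits in the red column, and reaching amber at 50% takes strong assumptions, such as 30% awareness in the public, 70% in the enriched channels and half of responses from those channels.

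Criterion 33 is one of 17 criteria listed in row 34 apart from that row itself. Row 35 takes it in only through row 34, and a red score leads to review rather than stopping. The consequence is therefore limited.

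Finally, question order and the recording of source could be left to the questionnaire or a statistical analysis plan, so their absence is not the fault. The fault is the distribution route that the protocol fixes. A later analysis could separate the sources only if they had been recorded.

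The two population descriptions could be read as where people are sought and who is eligible. They still leave open which population the percentage describes.

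**Conclusion.** The point holds for the sampling frame. Distribution through the promotion networks and the intervention pharmacies over-represents people likely to have been exposed, and this component raises measured awareness whenever awareness is higher in those channels. That condition is plausible, especially for the pharmacies, but it is an assumption. The size cannot be computed from the documents; the figures above only illustrate that the effect could exceed the sampling error at 600 responses. The net direction of error is not established. As planned, the percentage cannot safely be read as awareness in the wider community, and criterion 33 would be scored on it. This is worth correcting before the survey is fielded, but it does not threaten the study.

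**What to change.** - In step F.3, have the source recorded on every response, with a separate link or QR code for each of: intervention pharmacies; promotion networks or social media; passers-by approached by students.
- In criterion 33, score awareness on responses not obtained through the intervention pharmacies. Take the passers-by approached in general community settings as the main estimate, and report awareness by source beside it. Do not restrict them to venues without promotion: that would select for non-exposure and bias the figure downwards.
- Keep all responses for the acceptability and accessibility items.
- Make the Study Summary and the eligibility criteria for the general public name the same target population.

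No second survey during delivery is proposed, because it would need a separate instrument and fieldwork.

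The cost is a few survey links, wording changes through the amendment process, and a wider interval because awareness rests on fewer than 600 responses. If 400 responses remained, the 95% half-width would be 2.9 points at 10% awareness and 4.5 at 30%. With 300 it would be 3.4 and 5.2, against 2.4 and 3.7 with 600. The counts of 400 and 300 are assumptions. Source must be recorded at collection, since it cannot be reliably reconstructed afterwards.

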#### Quantitative data

There are three sets of quantitative data: the evaluation of pharmacy staff learning, the intervention measures and the community e-survey. To assess the impact on pharmacy staff learning (using the CPD Reaction Questionnaire), baseline and post-training data scores will be compared. For both the CPD Reaction Questionnaire and the community e-survey, categorical variables will be analysed using the chi-squared test or Fisher's exact test as appropriate. Continuous data will be analysed using the within-group t-test or Wilcoxon signed rank-test as appropriate. Statistical significance will be assessed at the 5% (two-sided) level. All statistical analyses will be conducted using IBM Statistical Package for Social Sciences (SPSS) 22.

All client and pharmacy intervention / control data will be processed using R Version 3. The demographics and characteristics of the samples will be initially summarised using frequencies and percentages for categorical variables and mean and standard deviation (if normally distributed) or median and interquartile range (if not normally distributed) for continuous variables.

The main outcome in this feasibility study is the number of community pharmacy consultations for people enquiring about or seeking support for domestic violence or suicidal ideation per issue and level of severity. Descriptive comparisons will be made between intervention and control pharmacies. Appropriate multivariable linear regression models will explore differences between intervention and control groups in means and 95% CIs. As the feasibility study is not powered to detect effectiveness, the focus will be on whether 95 % CIs include a meaningful difference. This will seek to inform a sample size calculation for a future definitive trial.

The final evaluation of feasibility will involve the integration of the qualitative and quantitative data and will include an economic evaluation. In the economic analysis, a societal perspective will be taken into consideration. Business data including staff time will be used to inform the findings. Cost per client will be estimated by dividing the costs of the response service by the total number of clients accessing the service in the intervention group. An incremental cost-effectiveness ratio (ICER) will be determined to explore the affordability and potential cost-effectiveness of the intervention and inform a future trail rather than provide a definitive comparison

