#### Size of sample

The sample size for the qualitative elements of the study will enable us to capture both a wide range of views and diverse perspectives to enable us to meet the objectives of the study.

This is a feasibility study so the sample size for the number of pharmacies has been pragmatically determined and to ensure sufficient data can be collected so the objectives of the research can be met.

For the e-survey, we compute that the estimated proportion of people who would say yes (i.e. are aware of the service) will be between 10% (precision 8.3% - 11.7%) and 30% (precision 27.4% to 32.6%) with a p-value for 95 confidence interval set at 0.05.

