#### 4. Public survey

Participants for the e-survey will be identified through distribution by local community venues, such as supermarkets, post offices, sports venues, faith venues etc.

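### The e-survey's awareness precision and tests assume independent responses, although respondents are reached through the venues, networks and pharmacies that promote the service (minor)

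*Protocol*

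**What the plan says.** **Collection.** Section F.3 (Public e-survey) states "A total of 600 responses will be aimed for" and "Assuming a response rate of 50%, 1200 people will need to be specifically targeted". It distributes the survey through the community networks used for promotion and through the intervention pharmacies, and employs students for "approaching passers-by in community settings and promoting on social media". The Recruitment section (4. Public survey) adds "distribution by local community venues, such as supermarkets, post offices, sports venues, faith venues etc". The Study Summary describes the population as "E-survey: General public in locality of intervention pharmacies". The eligibility criteria accept any adult resident of Lincolnshire, and the study flowchart describes wide electronic distribution by social media.

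**Promotion.** Section E (Implementation of Intervention) promotes the service in supermarkets, sports centres, religious venues and similar places, and on social media. It also uses a press release, a radio advert and a website.

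**Precision.** Size of sample expects awareness in the range "10% (precision 8.3% - 11.7%) and 30% (precision 27.4% to 32.6", at the 95% level.

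**Analysis.** Quantitative data says that for the e-survey "categorical variables will be analysed using the chi-squared test" or Fisher's exact test, at the two-sided 5% level. F.3 says the comparisons are between demographic groups. The protocol mentions no design effect, no identifier for venue or channel and no allowance for clustering.

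**Use.** Appendix 1, criterion 33, grades awareness in bands set at 70%, 50% and 30%.

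**The concern.** The main thing the survey measures is whether a person has heard of the service, and the survey finds people through the channels that told them about it. Two respondents met at the same supermarket or in the same town share their exposure to the promotion, so their answers are probably more alike than those of two people drawn at random. A plain binomial interval ignores this. With positive correlation its real coverage is below 95%. A chi-squared test also loses its nominal level to the extent that the characteristic tested follows venue or locality.

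At stake are the stated reliability of the awareness estimate and the reading of some group comparisons. Timing also matters: an analysis can allow for clustering only if the source of each response was recorded in the field, and it cannot be recovered later.

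**Working it through.** **1. Reproduce the stated precision.** The half-width is 1.96 × √(p(1−p)/n).

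- n = 600 (responses): 1.96 × √(0.09/600) = 2.4 points at 10%, giving 7.6% to 12.4%; 1.96 × √(0.21/600) = 3.7 points at 30%, giving 26.3% to 33.7%. These do not match the protocol.
- n = 1200 (people approached): 1.7 points at 10%, giving 8.3% to 11.7%; 2.6 points at 30%, giving 27.4% to 32.6%. These match exactly.

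The printed intervals are therefore simple binomial intervals on the number approached. On the 600 planned responses they are √2 = 1.41 times wider, even with full independence. That denominator error is separate from clustering, so the baseline from here on is n = 600.

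**2. Add clustering.** With k equal clusters of m = 600/k responses and intracluster correlation ICC, the design effect is DE = 1 + (m − 1) × ICC and the half-width is multiplied by √DE. Both k and the ICC are assumptions. The only anchor in the protocol is the set of 8 intervention pharmacies, whose localities the Study Summary names; 600/8 = 75.

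| Clusters (m) | DE at ICC 0.01 / 0.02 / 0.05 | Half-width at 30% awareness, points |
|---|---|---|
| Independent | 1 | 3.7 |
| 40 venues (15) | 1.14 / 1.28 / 1.70 | 3.9 / 4.1 / 4.8 |
| 20 venues (30) | 1.29 / 1.58 / 2.45 | 4.2 / 4.6 / 5.7 |
| 8 localities (75) | 1.74 / 2.48 / 4.70 | 4.8 / 5.8 / 7.9 |

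These figures use the normal quantile. With only 8 clusters a t quantile on 7 degrees of freedom (2.365) is more honest: at ICC 0.02, 5.8 × 2.365/1.96 = 7.0 points.

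**3. Level of the unadjusted 5% test.** Simulation under no true group difference: 20 venues of 30, awareness 30%, beta-binomial responses, 10,000 runs per cell.

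| How the group relates to venue | ICC 0.01 | ICC 0.02 | ICC 0.05 |
|---|---|---|---|
| Balanced within every venue | 5.0% | 4.9% | 5.5% |
| Mix varies between venues | 5.5% | 6.4% | 8.8% |
| Fully determined by venue | 8.4% | 11.7% | 20.9% |

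A characteristic such as sex, if mixed within venues, behaves like the first row. A characteristic that differs strongly between venues or localities moves towards the third.

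**The case against.** The strongest reply is that the cluster structure is assumed. The list of venues is open-ended, distribution is also electronic and county-wide, and radio, press and website promotion is not tied to a venue. With many small sources or a very small ICC, the design effect is close to 1. This stands, and it is why no single corrected figure can be given.

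Three stronger readings are tempting and are not supported:

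- **That the survey uses few venues, or 8 clusters.** The protocol sets no limit and gives no count. Eight localities is one scenario, and social-media respondents need not belong to any of them.
- **That the 5% tests reject too often in general.** Applying 2 × (1 − Φ(1.96/√DE)) to the 8-locality scenario gives actual levels of about 14% to 37%, but only for a factor fixed by locality. The planned comparisons are between demographic groups, which can mix within venues, and then the level stays near 5%.
- **That the progression decision is at risk.** Criterion 33 uses point estimates in bands 20 points apart. No interval enters the rule, and a red result leads to review. A wider interval matters only when awareness lies near a cut-off.

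It is also fair to say that an adjusted variance could be set in a statistical analysis plan, and that this is a descriptive part of a feasibility study. The first does not help if the source was never recorded. The second bears on severity. Finally, a convenience sample taken through the promotion channels may be biased for awareness, and no interval width reflects that.

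**Conclusion.** The point holds in a conditional form and is minor. The protocol plans collection through the channels that create awareness, while its precision statement and named tests assume independence. If the correlation within venue or locality is positive, the error is in one direction: intervals too narrow, and some tests above 5%. At 30% awareness and 600 responses, ICCs of 0.01 to 0.05 raise the half-width from 3.7 points to between 3.9 (40 venues) and 7.9 (8 localities). The venue counts, equal cluster sizes and ICCs are all assumptions. Clustering does not explain why the printed intervals are narrow; the use of 1200 in place of 600 does. Clustering would widen the corrected intervals further.

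**What to change.** 1. Before fieldwork, give each venue, pharmacy and online channel its own survey link or code, and ask for part-postcode so that online responses can be placed in a locality.
2. Report awareness with a cluster-adjusted 95% interval beside the simple one, t-based or otherwise small-sample corrected if clusters are few.
3. Use clustered tests for characteristics that follow venue or locality. The named tests can stay for characteristics mixed within venues.
4. Restate Size of sample for 600 responses: ±2.4 points at 10% and ±3.7 points at 30% if independent, followed by a stated range of design effects and the assumptions behind it.
5. State that none of this removes selection bias from surveying through the promotion channels.

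The cost is slightly more set-up and analysis, and a less favourable stated precision. No extra respondents are needed.
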